9.1.6. AEs of Special Interest

The following AEs of special interest are noted: nausea, vomiting, constipation, somnolence, sedation, dizziness and vertigo. For each of these AEs, summary tables of incidence and prevalence will be prepared that look at the number of days from the start of treatment until first onset and duration of the AE in days for all patients and by gender.

The summary of TEAEs by severity will be repeated for each AE of special interest overall and for the Treatment Period and Washout and Safety Follow-up Period. The severity that will be presented represents the most extreme severity captured on the eCRF page (Grade 1 through Grade 5 with Grade 5 being the most severe). A patient with two or more AEs within the same level of summarization will be counted only once in that level using the most severe incident. TEAEs that are missing severity will be presented in tables as “Severe” (i.e. Grade 3) but will be presented in the data listing with a missing severity. Percentages will be calculated out of the number of patients in the safety population. For an AE that is reported during more than one of these periods, the earliest period of onset will be used in the incidence calculation. Additionally, the summary will also be repeated for the Titration Period. Since the Titration Period is a subset of the Treatment Period, AEs will be reported in both periods, where applicable.

9.1.7. Abuse-Potential Related AEs

Although nalbuphine is not a controlled substance in the US or Europe, AEs of special interest that suggest a possible addiction or abuse potential or withdrawal will be specifically analyzed to screen for these effects. These AEs, obtained from the list provided by Love et al (2013) [see [Section 13.2](#)] will be designated as such in the study data base.

The overview AE summary will be repeated for abuse-potential related AEs. Summary tables of incidence and prevalence for these events will be prepared that look at the number of days from the start of treatment until first onset and duration of the AE in days for all patients and by gender.

The summary of TEAEs by severity will be repeated for abuse-potential related AEs overall and for the Treatment Period and Washout and Safety Follow-up Period. The severity that will be

presented represents the most extreme severity captured on the eCRF page (Grade 1 through Grade 5 with Grade 5 being the most severe). A patient with two or more AEs within the same level of summarization will be counted only once in that level using the most severe incident. TEAEs that are missing severity will be presented in tables as “Severe” (i.e. Grade 3) but will be presented in the data listing with a missing severity. Percentages will be calculated out of the number of patients in the safety population. For an AE that is reported during more than one of these periods, the earliest period of onset will be used in the incidence calculation. Additionally, the summary will also be repeated for the Titration Period. Since the Titration Period is a subset of the Treatment Period, AEs will be reported in both periods, where applicable.

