13.2. List of Abuse-Potential Associated Adverse Events

From Love et al (2013): "Proposed Query to Capture Abuse-Associated Adverse Events,"
College on Problems of Drug Dependence, 75th Annual Meeting, San Diego, CA

***** SELECTED ABUSE-RELATED ADVERSE EVENTS *****;
"Abnormal behaviour", "Abnormal dreams", "Abnormal sleep-related event",
"Accidental death", "Accidental overdose", "Accidental poisoning", "Acute psychosis", "Affect
lability", "Affective disorder", "Aggression", "Agitation", "Alice in wonderland syndrome",
"Altered state of consciousness", "Altered visual depth perception", "Amnesia",
"Amnestic disorder", "Amphetamines", "Amphetamines positive", "Analgesic therapy", "Anger",
"Anhedonia", "Anterograde amnesia", "Antisocial behaviour", "Antitussive therapy", "Anxiety",
"Anxiolytic therapy", "Apathy", "Asocial behaviour", "Asthenia", "Attention-seeking
behaviour", "Balance disorder", "Belligerence", "Benzodiazepine drug level", "Blunted affect",
"Bradyphenia", "Central nervous system stimulation", "Cognitive disorder", "Completed
suicide", "Compulsions", "Confabulation", "Confusional arousal", "Confusional state",
"Consciousness fluctuating", "Coordination abnormal", "Deja vu", "Delirium", "Delusion",
"Delusion of grandeur", "Delusion of reference", "Delusion of replacement", "Delusional
perception", "Delusional disorder, erotomatic type", "Delusional disorder, grandiose type",
"Delusional disorder, jealous type", "Delusional disorder, mixed type", "Delusional disorder,
persecutory type", "Delusional disorder, somatic type", "Delusional disorder, unspecified type",
"Delusions, mixed", "Dependence", "Depersonalization", "Depressed level of consciousness",
"Depressive delusion", "Derailment", "Derealisation", "Disinhibition", "Disorientation",
"Dissociation", "Dissociative amnesia", "Dissociative identity disorder", "Disturbance in
attention", "Disturbance in social behaviour", "Dopamine dysregulation syndrome",
"Dopaminergic drug therapy", "Drug abuse", "Drug abuser", "Drug dependence",
"Drug dependence, antpartum", "Drug dependence, postpartum", "Drug detoxification", "Drug
diversion", "Drug screen positive", "Drug tolerance increased", "Dyslogia", "Dysphoria",
"Elevated mood", "Emotional disorder", "Emotional distress", "Energy increased", "Erotomanic
delusion", "Euphoric mood", "Executive dysfunction", "Fear", "Feeling abnormal", "Feeling
drunk", "Feeling jittery", "Feeling of despair", "Feeling of relaxation", "Flashback", "Flat affect",

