"Flight of ideas", "Formication", "Hallucination", "Hallucination, auditory", "Hallucination,
gustatory", "Hallucination, olfactory", "Hallucination, synaesthetic", "Hallucination, tactile",
"Hallucination, visual", "Hallucinations, mixed", "Hangover", "Homicidal ideation",
"Homicide", "Hostility", "Hypervigilance", "Hypnagogic hallucination",
"Hypnopompic hallucination", "Ideas of reverence", "Illogical thinking", "Illusion",
"Impaired driving ability", "Impaired reasoning", "Impulsive behaviour", "Inappropriate affect",
"Incoherent", "Intentional drug misuse", "Intentional overdose", "Intentional self-injury",
"Irritability", "Jamais vu", "Jealous delusion", "Judgement impaired", "Loose associations",
"Magical thinking", "Mania", "Maternal use of illicit drugs", "Memory impairment", "Mental
disability", "Mental disorder", "Mental impairment", "Mental status changes", "Miosis", "Mood
altered", "Multiple drug overdose", "Multiple drug overdose accidental", "Multiple drug
overdose intentional", "Muscle relaxant therapy", "Mydriasis", "Nasal necrosis", "Nasal septum
perforation", "Nasal septum ulceration", "Needle track marks", "Neonatal complications of
substance abuse", "Overdose", "Panic attack", "Panic reaction", "Paramnesia",

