"Paranoia", "Parasomnia", "Paroxysmal perceptual alteration", "Persecutory delusion", "Personality change", "Personality disorder", "Physical assault", "Poisoning", "Polysubstance dependence", "Prescription form tampering", "Product tampering", "Product used for unknown indication", "Psychomotor hyperactivity", "Psychomotor retardation", "Psychomotor skills impaired", "Psychotic behaviour", "Psychotic disorder", "Reactive psychosis", "Restlessness", "Retrograde amnesia", "Sedation", "Self-injurious behaviour", "Self-injurious ideation", "Sensory disturbance", "Sensory level abnormal", "Sleep sex", "Sleep terror", "Slow speech", "Somatic delusion", "Somatic hallucination", "Somnolence", "Staring", "Steroid withdrawal syndrome", "Stupor", "Substance abuse", "Substance abuser", "Substance use", "Substance-induced mood disorder", "Substance-induced psychotic relief", "Suicidal behaviour", "Suicidal ideation", "Suicide attempt", "Suspiciousness", "Tangentiality", "Thinking abnormal", "Thought blocking", "Thought broadcasting", "Thought insertion", "Thought withdrawal", "Toxicity to various agents", "Transient global amnesia", "Transient psychosis", "Treatment noncompliance", "Urine amphetamine", "Urine amphetamine positive", "Violence-related symptom"

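### SAP Section 9.1.7 sets out to screen for withdrawal, but its Section 13.2 term list has no opioid or general drug withdrawal term, so an event coded that way is not flagged

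*SAP*

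**What the plan says.** Section 9.1.7 gives the purpose of this analysis: "AEs of special interest that suggest a possible addiction or abuse potential or withdrawal will be specifically analyzed to screen for these effects". It obtains the events from a published list reproduced in Section 13.2 and says that they "will be designated as such in the study data base". It names no further search and no other source of terms.

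Section 13.2 gives the title of the source as "Proposed Query to Capture Abuse-Associated Adverse Events" and sets the terms out as quoted strings separated by commas.

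The outputs planned for the flagged events are the AE overview, incidence and prevalence tables with days from start of treatment to first onset and duration (all patients and by gender), and a severity summary. The severity summary is given overall and for the Treatment, Washout and Safety Follow-up, and Titration Periods.

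Withdrawal is also addressed elsewhere. Section 9.2.1 has patients complete the SOWS daily for two weeks after stopping drug and summarises its 16 symptoms day by day. Section 9.1.1 tabulates all TEAEs by SOC and PT and lists all AEs.

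**The concern.** The purpose in Section 9.1.7 is wider than the list that carries it out. The purpose names three things: addiction, abuse potential and withdrawal. The list was built for abuse. When a fixed list decides which events are flagged, an event outside it does not enter the tables, whatever the introductory sentence intends.

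The event at issue is the most explicit one: an investigator records withdrawal after the study drug is stopped, held or reduced, and the coder assigns an opioid or drug withdrawal term. The primary objective is safety over up to 50 weeks of treatment, so the analysis that says it screens for this effect should pick that event up. As written, a count from Section 9.1.7 says nothing about events so coded.

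**Working it through.** No sample size, power or error rate is involved. The check compares the stated purpose with the contents of the list.

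1. **Contents of the list.** Section 13.2 was split into its terms: 213 entries, all distinct. Each was searched for word stems that a withdrawal term might contain.
   - *withdraw*: 2 (*Steroid withdrawal syndrome*, *Thought withdrawal*)
   - *opioid*: 0; *opiate*: 0
   - *rebound*: 0; *abstinence*: 0; *discontinu*: 0
   - *detox*: 1 (*Drug detoxification*)
   - *depend*: 5 (dependence terms)

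2. **What the two hits mean.** "Steroid withdrawal syndrome" is a withdrawal term, but not for an opioid or for the study drug. *Thought withdrawal* is a psychiatric symptom. That leaves 2 − 2 = 0 terms for opioid or general drug withdrawal.

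3. **Where such terms would stand.** The list is close to alphabetical. It passes from *Drug tolerance increased* to *Dyslogia*, and it ends at *Violence-related symptom*. There is no entry beginning with drug withdrawal or with withdrawal at either place.

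4. **What the list would still catch.** *Agitation*, *Anxiety*, *Dysphoria*, *Feeling jittery*, *Irritability*, *Mydriasis* and *Restlessness* are all listed. A withdrawal reaction coded by such symptoms would be flagged, but the tables would not identify it as withdrawal.

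5. **Timing of onset.** Section 9.1.7 counts days to onset from the start of treatment only. The period split does not replace onset after last dose:
   - For patients who complete treatment through Visit 14, Section 9.1 fixes the washout window at first dose + 350 to + 363 days. This suits 50 weeks of drug (50 × 7 = 350 days).
   - Section 3.1 caps Observation plus Treatment at 50 weeks. A patient with 12 weeks of observation therefore has at most 50 − 12 = 38 weeks on drug. That is 38 × 7 = 266 days, so the two weeks after last dose run from about first dose + 266 to + 279, before the fixed window opens.
   - For patients who stop drug before Visit 14 but remain on study, all AEs from first dose onward count as Treatment Period events.

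6. **Spelling, a separate check.** Five entries look corrupted:
   - *antpartum* stands beside a correctly spelled *postpartum* entry.
   - *erotomatic type* contrasts with *Erotomanic delusion* in the same list.
   - "Ideas of reverence" contrasts with *Delusion of reference* in the same list.
   - "Substance-induced psychotic relief" follows *Substance-induced mood disorder* and does not read as a diagnosis.
   - *Bradyphenia* also appears misspelled.

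   None of the five is a withdrawal term.

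**The case against.** The best reply is that the plan does not depend on this list to detect withdrawal. Daily SOWS change during washout is a secondary objective and endpoint. Section 9.2.1 reports each symptom on each of 14 days, the total score, the highest total by category and the worst symptom score, and patients who stop early are included. A coded withdrawal event would also appear in the SOC and PT tables and in the AE listing, and in the discontinuation and SAE outputs where those apply. The heading of Section 9.1.7 and its outputs refer to abuse potential, so no table is labelled as a withdrawal result.

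Most of this stands, and it limits the size of the point. It does not remove the mismatch. The SOWS is a questionnaire that starts at the end of treatment or at premature discontinuation. Section 3.4 allows dose reductions and holds during treatment, and the SAP describes no SOWS at those times. The general tables would show the event, but they do not give the time-to-onset and duration summaries promised in Section 9.1.7.

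A reader might infer that withdrawal can never appear in the Section 9.1.7 tables, or that the screen has zero sensitivity. The documents do not support that, because symptom-coded events are on the list; the exclusion applies only to an event coded under an opioid or general drug withdrawal label. A reader might also infer that the misspellings cause the gap, or that those entries can never match. They concern other terms, and the SAP does not fix the matching method. Some of them may come from the cited source or from reading the PDF.

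**Conclusion.** The point holds in a limited form. Section 9.1.7 announces a screen for withdrawal, and the list that implements it has 0 of 213 terms for opioid or general drug withdrawal. An event coded directly to such a term would be omitted from every table in that section. The effect is confined to this one grouped analysis. It does not show that withdrawal goes unassessed in the study, and nothing in the SAP shows that a zero in these tables would be presented as evidence of no withdrawal.

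The conclusion assumes that the list is applied as written, without an added search, that Section 13.2 is complete as printed, and that the MedDRA version used (left to the study report) has terms for drug withdrawal to which an investigator's report could be coded. The last assumption must be checked in the dictionary.

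The corrupted entries are a separate, minor defect. They matter only if flagging uses exact string matching, which the layout of the appendix suggests but Section 9.1.7 does not state. The mismatch should be corrected before database lock.

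**What to change.** Add the drug-withdrawal terms of the MedDRA version in use to Section 13.2 as a separately labelled withdrawal subgroup, and refer to it in Section 9.1.7. Tabulate that subgroup by onset relative to last dose as well as from start of treatment. Keep the published abuse list as its own group, so that its source remains clear. If the sponsor does not want a withdrawal subgroup, the lesser remedy is to remove withdrawal from the stated purpose of Section 9.1.7 and point to the SOWS analysis in Section 9.2.1.

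Separately, check all 213 entries against the dictionary version before lock, correct those that do not match, and state how events are matched to the list.

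The cost is one appendix edit, one dictionary check and a small table. The downside is a few more flagged events. No new data are needed.

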9.1. Adverse Events

Details regarding the definition and reporting of an AE or a serious adverse event (SAE) are provided in the study protocol. AEs will be recorded starting with the signing of the first

informed consent. All AEs will be collected through the Washout and Safety follow up visit (or Early Termination Visit). Following the Washout and Safety follow up visit (or Early Termination Visit), all unresolved AEs that were reported by the Investigator to be probably drug related should be followed by the Investigator until the events are resolved, the patient is lost to follow-up, or the AE has stabilized.

Non-serious AEs that begin during the Observation Period will be captured as medical history in the TR03 extension study; patients who never transition from the Observation Period to the Treatment Period are screening failures and did not complete the early termination or end of study CRFs. SAEs occurring during the Observation Period will be recorded as SAEs.

Also, AEs that were ongoing at the time of a patient's completion of the TR03 core study are recorded as medical history in the TR03 extension study.

A treatment-emergent AE (TEAE) will be defined as one starting or worsening on or after the first dose of study medication during the extension study. If the start date is missing, the event is assumed to be treatment emergent.

For patients who complete study treatment through the Visit 14/End of Treatment visit, Titration Period AEs are those with an onset date from first dose date of the extension study through (first dose date + 27 days). Treatment Period AEs are those with an onset date from first dose date of the extension study through (first dose date + 349 days). Washout and Safety Follow-up AEs are those with an extension study onset date of (first dose date + 350 days) through (first dose date + 363 days). For patients who are treated and who discontinue study drug use prior to the Visit 14/End of Treatment visit yet remain on-study, AEs with an onset date on or after the first dose date of the extension study will be considered Treatment Period AEs.

For the purpose of inclusion in TEAE table summaries, incomplete AE onset and end dates will be imputed as described below.

For incomplete AE onset dates:

- If the day is missing but the month and year are known:
 - If the month and year are different from the month and year of the first dose of study drug, then use the first day of the month as the imputed onset date.

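### Section 9.1.7 screens adverse events for withdrawal but times onset only from first dose, so no AE table shows onset relative to last dose

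*SAP*

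**What the plan says.** Section 9.1.7 states its purpose: "AEs of special interest that suggest a possible addiction or abuse potential or withdrawal will be specifically analyzed to screen for these effects". The events are the preferred terms listed in Section 13.2. For timing, the section plans incidence and prevalence tables, overall and split by gender, to "look at the number of days from the start of treatment until first onset and duration of the AE in days". Section 9.1.6 uses the same clock for its seven named events: "number of days from the start of treatment until first onset and duration of the AE in days for all patients and by gender".

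Which events enter is settled in Section 9.1: "A treatment-emergent AE (TEAE) will be defined as one starting or worsening on or after the first dose of study medication during the extension study". No upper limit is tied to the last dose, and collection runs through the Washout and Safety Follow-up visit.

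Section 9.1 also defines the periods. For patients who complete treatment, "Treatment Period AEs are those with an onset date from first dose date of the extension study through (first dose date + 349 days"), and Washout AEs are those from first dose +350 to +363 days. For treated patients who stop drug early but stay on study, every AE from first dose onward is assigned to the Treatment Period. The overview summary (Sections 9.1.1 and 9.1.7) and the severity summaries (Sections 9.1.6 and 9.1.7) are split by these periods. The onset and duration tables are not.

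**The concern.** Withdrawal is a matter of time since the last dose. A table that counts only from the first dose cannot show whether terms on the Section 13.2 list, such as anxiety, agitation or restlessness, cluster in the first days off drug, because patients stop at very different times. The same table mixes onsets on drug with onsets after stopping, so it is not a clean description of onset during treatment either. Because only the first onset is timed, a patient with anxiety during titration and again after stopping contributes only the titration date.

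One would look to the by-period tables to make up for this. Their periods, however, are also counted from first dose, so they separate washout events only for some patients. Safety and tolerability are the primary objective of the study (Section 2.1), and the AE screen for withdrawal is one of its named safety analyses.

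**Working it through.** **Inputs**

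- Treatment lasts up to 50 weeks and washout 2 weeks (Section 3.1).
- Observation lasts up to 12 weeks, and observation plus treatment together at most 50 weeks (Section 3.1).
- The failure-to-improve rule can stop drug from Treatment Visit 3 (Section 3.2.1), which is the Week 5 visit (Section 7.3.1).
- AE periods are as defined in Section 9.1.
- Study day is the date minus the first dose date, plus 1 (Section 4.2).

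**1. The plan's own windows.** 50 × 7 = 350 days, so the last treatment day is first dose +349 (study day 350). Washout is 2 × 7 = 14 days, first dose +350 to +363 (study days 351 to 364). The windows reproduce for a patient with 50 weeks on drug.

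**2. Onset day of the same event, three days after last dose.** Onset day = 7 × (weeks on drug) + 3.

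| Drug stops at end of | Onset day as tabulated |
|---|---|
| Week 5 | 35 + 3 = 38 |
| Week 26 | 182 + 3 = 185 |
| Week 50 | 350 + 3 = 353 |

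The distance from last dose is three days in each row, and the planned table cannot show that. The stopping weeks are illustrations. Section 3.2.2 allows stops for other reasons, which can come before Week 5.

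**3. How many true washout days the Washout window catches.** Take a completer with *k* weeks of observation who then uses all the remaining time on drug.

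- Last dose is on study day *d* = 7 × (50 − *k*) = 350 − 7*k*.
- True washout is days *d* + 1 to *d* + 14.
- Days falling in the fixed window 351 to 364 = max(0, 14 − 7*k*).

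| Observation weeks | Last dose, study day | True washout, study days | Counted as Washout |
|---|---|---|---|
| 0 | 350 | 351–364 | 14 of 14 |
| 1 | 343 | 344–357 | 7 of 14 |
| 2 | 336 | 337–350 | 0 of 14 |
| 12 | 266 | 267–280 | 0 of 14 |

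From *k* = 2 to *k* = 12 the count is 0, and every true washout day is labelled Treatment Period.

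**4. Early discontinuers who remain on study.** Section 9.1 assigns all their AEs from first dose onward to the Treatment Period, so 0 of 14 washout days count as Washout. Section 3.2.1 nevertheless sends failure-to-improve patients to the washout assessment two weeks later, so their post-stop events are collected.

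**5. Is the date available?** Yes. Section 7.3.2 takes the last dose date from the study completion page, and uses the visit at which drug was last returned if it is missing or the patient is lost to follow-up.

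**The case against.** The best defence is that the SAP has a dedicated withdrawal analysis. Section 9.2.1 summarises the 16 SOWS items and the total score on each of 14 days from the End of Treatment visit. Patients who stop early also complete the scale daily for two weeks after their last dose. A reader might infer from Section 9.1.7 that the timing of withdrawal after stopping is never shown. That is not so: symptoms are displayed day by day on a post-cessation clock. But SOWS is a self-rated scale. It does not time reported AEs or give their duration, and the SAP chose to screen AEs for withdrawal in addition to it.

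Second, the overview and severity tables are split by period, and for patients with 50 weeks on drug the split is exactly right. That stands for those patients only. Where the split fails, the cause is the period definition in Section 9.1, so rewording Section 9.1.7 alone would not repair it.

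Third, Section 9.1.6 claims no withdrawal screen, and nausea and vomiting are not on the Section 13.2 list. That is correct. For Section 9.1.6 the point is only that on-drug and post-stop onsets are pooled.

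Fourth, the study is a single descriptive group, the first-dose clock is clear and reproducible, and the AE and exposure listings let a reader work out days since last dose case by case. This limits the consequence. It does not make the planned table answer its stated question.

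**Conclusion.** The point holds in a limited form. The AE screen for withdrawal uses a clock that cannot show withdrawal timing, pools onsets before and after stopping, and leaves post-stop recurrences untimed. No AE table counts days from last dose. The by-period tables make up for this fully only after 50 weeks on drug. They catch 7 of 14 washout days after one week of observation, and none after 2 to 12 weeks or for early discontinuers who stay on study. These counts assume whole weeks of observation and drug taken to the 50-week combined limit.

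Two stronger readings are not supported. Post-stop events do not in general appear as very late onsets: that describes long-treated patients, while an early stopper's event looks like an ordinary early onset (day 38 above). Nor can one say how far the pooled onset statistics would shift, or what share of patients is affected. The SAP gives no event counts, discontinuation rates or rates of entry through observation. The overall count of patients with any treatment-emergent AE is unaffected. What suffers is timing and the assignment to periods. It is worth correcting before database lock.

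**What to change.** 1. **Section 9.1.7:** limit the table of days from first dose to onsets on or before the last dose. Add a table for onsets after the last dose, giving days from last dose to the first post-dose onset and its duration, whether or not the term had already occurred on drug.
2. **Section 9.1.6:** apply the same last-dose cut to its onset table.
3. **Section 9.1:** define the Washout AE window from each patient's last dose date (the 14 days after it), for completers and for early discontinuers who remain on study. Carry this through the by-period overview and severity tables.

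The cost is SAP wording, reprogramming of the period flag, and one extra table from dates already collected. One detail needs a rule. The date imputation in Section 9.1 generally sets a missing onset day to the first of the month, which in the month of the last dose would place a post-stop event on drug. Such cases should be flagged or given their own convention. Last dose dates taken from the drug-return visit are less exact and should be marked in the listing.
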